7.1 Statistical Analysis plan	
7.2 Sample Size Calculation & Power Analysis	
7.3 Sample Processing and Analyses	
7.4 Grouping	15
8.0 Ethical Considerations	16

9.0 Dissemination of Data	16
10.0 References	17

Table of Events

Procedure	Visit 1	Visit 2
informed consent	Х	
medical history	Х	
list of medications	Х	
measure height	Х	
measure weight	Х	
DEXA scan ¹	Х	Х
In Body scan ¹	Х	Х
Dominant handgrip strength	Х	
5-rep chair stand	Х	
10-meter gait speed	Х	
SARC-F questionnaire	Х	
periodic blood sampling		Х
frequent breath sampling		Х
ingest study product		Х

¹If subject meets the requirements to perform the DEXA scan and In Body scan on visit 1, these tests will be performed at that time. If they do not, these tests will be performed at Visit 2.

1.0 Background and Rationale

1.1 Introduction:

Sarcopenia increases the risk of a number of deleterious health conditions and represents a major financial cost to our healthcare system. Among older adults who are hospitalized, those with sarcopenia on admission are 5-fold more likely to incur higher hospital costs than those without (1). The operational definition of sarcopenia is defined as meeting the criteria for all of the following: low muscle strength, low muscle quantity or quality, and low physical performance. The diagnosis of sarcopenia requires techniques that are both expensive and operator-dependent. Simple measurements, such as BMI, do not necessarily identify sarcopenia. Importantly, current techniques can only identify sarcopenia after a physical/functional impairment has occurred. Skeletal muscle amino acid kinetics predict muscle health and functionality (2). Altered amino acid kinetics lead to decrements in muscle

mass, quality, and performance. Our laboratory, as well as others, have documented that the muscle response to circulating essential amino acids (EAA) determines muscle amino acid kinetics (2). Thus, we propose to characterize skeletal muscle amino acid kinetics to an EAA challenge, i.e., an oral amino acid tolerance test (OATT), in order to determine the state of muscle health. Analogous to the oral glucose tolerance test (OGTT) used to characterize alterations in glucose metabolism, the proposed OATT represents a potential low-cost solution to classifying patients' skeletal muscle health. The extrapolation of this work is the development of a simple analytical tool that would provide clinicians the ability to discern alterations in muscle amino acid kinetics prior to a loss of function.

1.2 Previous research on the topic

The rate of loss of muscle with aging in any given individual is variable and may be influenced by genetic factors, level of activity, amount of protein in the diet, total body weight, and occurrence of serious diseases that directly affect muscle mass and function. Nonetheless, the estimate from cross-sectional data that between 0.5-1.0 % of muscle mass is lost per year after the age of 70 years is reasonable (3). The physiological basis for loss of muscle over time results from an imbalance between the rates of muscle protein synthesis and breakdown. Consumption of dietary protein results in the absorption of amino acids and the activation of protein synthetic processes throughout the body, particularly muscle protein synthesis (4). There is a direct relationship between the amount of dietary protein intake and the net gain in body protein in young healthy individuals (5). Anabolic resistance refers to the circumstance in which dietary protein has a diminished stimulatory effect on the net production of new muscle protein. Critical illness (6) or the response to a major burn injury (7) provide clear-cut examples of anabolic resistance. In anabolic resistance associated with these pathological conditions, the normal linear relationship between dietary protein intake and net protein synthesis is capped, meaning that beyond a certain level of protein intake there is no further gain in net protein balance. For example, beyond a level of protein intake of 1.1 g protein/kg/day there is no net gain in body protein in critically ill patients (6). Once the maximal rate of protein synthesis is reached, there is no further gain in net protein synthesis, as the rate of protein breakdown is not affected by dietary protein consumption in severely catabolic patients. The

consequence of exceeding the amount of dietary protein intake that maximizes the net gain in body protein is the oxidation of the "extra" amino acids. As a result of the oxidation of a large percentage of dietary amino acids, urea and ammonia production increase significantly (7). Since this clinical population often has multi-organ failure, including impaired kidney function, an increase in urea and ammonia production can have adverse physiological consequences. Aging-related anabolic resistance is different than anabolic resistance associated with critical illness. Differences in the basic metabolic responses of protein metabolism in the two circumstances can explain the basis for the different nature of anabolic resistance. In critical illness, the loss of muscle protein is driven by a high rate of protein breakdown, which may be as much as 3 fold above normal (8). The high rate of protein breakdown floods the intramuscular pool with free amino acid precursors for protein synthesis, driving up the rate of protein synthesis. As a result, although protein synthesis is significantly less than the accelerated rate of breakdown in critical illness, protein synthesis is already driven close to the maximum rate without any intake of protein or amino acids (8). Since precursor supply is already high because of accelerated protein breakdown, provision of dietary protein or amino acids in critically ill patients has only a small effect on precursor availability and thus muscle protein synthesis. In healthy elderly individuals, basal rates of muscle protein synthesis and breakdown are not measurably different from younger individuals. As a result, protein synthesis can be increased by consumption of even small amounts of amino acids (9). In contrast, older adults are less responsive to the anabolic stimulus of low doses of amino acid or protein intake compared to younger individuals (10). Limited responsiveness of muscle protein synthesis at lower levels of intake but a similar maximal protein synthetic response suggests that the slope of the line relating the increase in muscle protein synthesis relative to increasing amounts of dietary protein consumption is less in elderly, but ultimately reaches the same maximum value as in younger individuals. However, behavior change, in this case increasing dietary protein to maximize muscle protein synthesis to blunt age-related losses of skeletal muscle, are difficult in elderly adults (11). Therefore, identification of individuals at risk for sarcopenia sooner in life are required. Considering changes in muscle protein kinetics precede functional outcome changes (e.g. muscle strength), assessment of postprandial amino acid metabolism represents a likely solution. The relationship between protein intake

Version #: 10 IRB# 262590 Page 6

Date: 31May22

and muscle protein synthesis has been demonstrated to be driven by the change in plasma essential amino acid concentrations (2). Stated another way, the changes in plasma essential amino acid concentrations following the ingestion of dietary protein drive the increase in muscle protein synthesis. The analogous parallel to amino acid and muscle is the use of the oral glucose tolerance test used to classify individuals with prediabetes and type-2 diabetes. Therefore, demonstrating that the essential amino acid response to an oral amino acid challenge can differentiate between elderly and young populations is a worthwhile first step in developing a new clinical diagnostic test to identify sarcopenia.

2.0 Hypotheses

We hypothesize that plasma amino acid response will be altered in elderly sarcopenic adults as compared to young and elderly healthy subjects.

We also hypothesize that the pharmacokinetics of plasma amino acids can be used to distinguish sarcopenic elderly from young and elderly healthy.

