3.0 Study Design and Procedures

We will enroll up to 35 subjects with a goal to study up to 30 healthy male and females: a group of 10 whose age is between 18 and 30 years, a group of 10 whose age is 70-89 years without the presence of sarcopenia, and a group of 10 whose age is 70-89 years with sarcopenia. We will use a 5-hour (one hour prior and 4 hours post-consumption of an amino acid supplement) period to completely characterize the plasma amino acid response to 10 grams of free-form essential amino acids of which 10% of the leucine content has been enriched with L-[1-13C] leucine. The principal end-point will be plasma amino acid response over the 4 hours following the consumption of the study product.

Secondary endpoints include body composition and total body water measurements. Small shifts in fluid from the extracellular to intracellular space likely correspond with EAA appearance and disappearance in plasma. BIA is a non-invasive, rapid assessment that is sensitive to acute shifts in fluid that are associated with disease and malnutrition states, such

Version #: 10 IRB# 262590 Page 7

Date: 31May22

Institution: UAMS

Sponsor: UAMS/TRI

as sarcopenia. As an exploratory analysis, we will measure acute shifts in total body,

intracellular, and extracellular fluid using multifrequency BIA throughout visit 2. This will serve

as preliminary data on a potential non-invasive method to evaluate muscle quality, anabolic

resistance, and a proxy indicator of sarcopenia.

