7.0 Data Analysis

7.1 Statistical Analysis plan

Means by which experimental data will be analyzed or interpreted: Changes in the plasma amino acids area under the curve (AUC), maximal amino acid concentration, change from basal to maximal amino acid concentrations, rate to maximal amino acid concentration, and the clearance rate of amino acids from the plasma will be assessed with an one-way ANOVA with appropriate post hoc testing. Statistical significance will be accepted at an alpha level of p ≤ 0.05 .

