7.2 Sample Size Calculation & Power Analysis

Statistical power and sample size are based on previous studies investigating differences in plasma amino acids in younger and older adults following the ingestion of 10 grams of free form essential amino acids (12). For peak EAA concentrations previous studies have demonstrated an effect size (Cohen's D) of 1.6 between health young and individuals with incipient sarcopenia. This effect size indicates we need 8 individuals in each group to detect a significant difference at an alpha level of 0.05 with 80% power.

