7.3 Sample Processing and Analyses

Blood samples will be processed and analyzed as described by PI's lab (2). Blood samples will be analyzed via LCMS to determine the concentration of specific amino acids relevant to the hypothesis. If performed, glucose and insulin concentrations will be performed using a COBAS analyzer. Stable isotope concentrations will be measured using either GC-MS or LCMS methods, if performed. Breath samples will be analyzed in real time via the collection apparatus. After all data has been analyzed and verified, samples will be discarded into a biohazard trash bag and disposed in accordance with UAMS biohazardous waste policy.

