7.4 Grouping

Subjects in the older groups will be divided into either sarcopenic or non-sarcopenic based on the results of the handgrip assessment at visit 1 and amount of lean tissue derived from the

body composition measurements. The thresholds (per the Sarcopenic Definitions and Outcomes Consortium) are as follows:

Men whose value is < 35.5 kg are considered to have low muscle strength. Women whose value is < 20 kg are considered to have low muscle strength.

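### Hypothesis 2 says amino acid kinetics can distinguish sarcopenic elderly, but 7.1 compares only group means and plans no measure of how well subjects are separated

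*Combined protocol and SAP*

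**What the plan says.** Section 2.0 gives two hypotheses. The first is that the plasma amino acid response is altered in sarcopenic elderly subjects. The second is separate: "We also hypothesize that the pharmacokinetics of plasma amino acids can be used to distinguish sarcopenic elderly from young and elderly healthy". Section 1.1 presents the oral amino acid test as a possible means of classifying patients' muscle health. Section 1.2 says that showing the response "can differentiate between elderly and young populations is a worthwhile first step in developing a new clinical diagnostic test to identify sarcopenia".

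Section 3.0 sets the end-point: "The principal end-point will be plasma amino acid response over the 4 hours following the consumption of the study product". Section 7.1 lists five quantities (AUC, maximum, change from basal to maximum, rate to maximum, clearance), which "will be assessed with an one-way ANOVA with appropriate post hoc testing" at p ≤ 0.05. It ranks none of them and mentions no ROC curve, cut-off, sensitivity, specificity or classification rule; nor does any other section. Section 7.3 describes the assay as serving "to determine the concentration of specific amino acids relevant to the hypothesis". Section 7.2 sizes the study on peak EAA, with an effect size "of 1.6 between health young and individuals with incipient sarcopenia", and does not call peak EAA the primary or lead parameter.

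**The concern.** A test of means asks whether group averages differ. To distinguish sarcopenic subjects from others is a claim about how far the distributions overlap. Followed as written, the plan would leave a p-value for a mean difference as the only evidence on hypothesis 2, and such a p-value can be significant while a large share of subjects fall on the wrong side of any cut-off. The study might then be reported as showing that the test distinguishes sarcopenia when no measure of separation had been planned.

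There is also a question of timing. A ROC analysis could be run later on the same data, but a guard against choosing the parameter and direction from the results exists only if both are fixed beforehand.

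**Working it through.** **Inputs.** 10 completers in each of three groups (3.0, 4.0); alpha 0.05 and five parameters (7.1); d = 1.6 and 8 per group at 80% power (7.2). Equal-variance normal data are assumed throughout.

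**The plan's own figure.** A two-sided two-sample t-test at d = 1.6 and 80% power needs 7.23 per group, rounded up to 8 (power 0.785 at 7, 0.845 at 8, 0.922 at 10). The stated 8 is reproduced. It is correct for a difference in two means and does not address discrimination.

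**Smallest significant contrast, 10 per group, 3 × 10 − 3 = 27 error df.**
- Unadjusted: d = t(0.975; 27) × √(2/10) = 2.052 × 0.447 = 0.918.
- Tukey: d = q(0.95; 3, 27)/√10 = 3.506/3.162 = 1.109.

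A separate two-group t-test on 18 df gives d = 0.940, which changes little.

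**Conversion to separation.** AUROC A = Φ(d/√2). Misclassification at the cut-off midway between the means = 1 − Φ(d/2).

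**Interval.** Hanley-McNeil variance for 10 versus 10: [A(1 − A) + 9(a − A²) + 9(b − A²)]/100, with a = A/(2 − A) and b = 2A²/(1 + A). On the logit scale, the SE is divided by A(1 − A).

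For d = 0.918: A = 0.742, SE = 0.113, logit = 1.055, logit SE = 0.113/0.1915 = 0.591. Then 1.055 ± 1.96 × 0.591 runs from −0.102 to 2.213, which back-transforms to 0.47 and 0.90.

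| Contrast | d | AUROC | SE | Logit 95% CI | Misclassified |
|---|---|---|---|---|---|
| Just significant, unadjusted | 0.918 | 0.74 | 0.113 | 0.47 to 0.90 | 32% |
| Just significant, Tukey | 1.109 | 0.78 | 0.105 | 0.52 to 0.92 | 29% |
| 7.2 effect size | 1.6 | 0.87 | 0.084 | 0.61 to 0.97 | 21% |

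The first two rows are significance thresholds, not expected effects.

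**Sarcopenic versus non-sarcopenic elderly.** The documents give no effect size for this contrast. Over an assumed range, d = 0.5 gives AUROC 0.64 (0.38 to 0.84), d = 0.8 gives 0.71 (0.45 to 0.89) and d = 1.2 gives 0.80 (0.54 to 0.93).

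**Why the logit scale.** In 40,000 simulated 10-versus-10 studies, plain 95% DeLong intervals covered 0.909 at AUROC 0.742 and 0.847 at 0.871. Logit-scale intervals covered 0.967 and 0.950.

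**Fixing the choice in advance.** Simulated chance that the AUROC reaches 0.75 with no true difference (10 versus 10, 40,000 runs):
- one parameter, direction fixed: 3%;
- one parameter, direction free: 6%;
- best of five, direction free: 28%, 23% and 17% at assumed correlations 0, 0.5 and 0.8.

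**The case against.** The best counter-argument is that the documents promise no diagnostic accuracy from this study. Section 1.2 speaks of differentiating populations and calls the work a first step; section 1.1 treats the clinical tool as an extrapolation. Hypothesis 1 concerns the response and hypothesis 2 the pharmacokinetics, so hypothesis 2 may simply ask whether the kinetic quantities in 7.1 also differ by group. ANOVA answers that. This reading is available, and it is why rewording the hypothesis is a sufficient remedy. It does not remove the point, because the text of hypothesis 2 and the classification language of 1.1 also support a claim about separating subjects, and the plan does not say which is meant.

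Under the normal model, the AUROC can also be derived from reported means and SDs. That is true, but the derivation depends on the model and leaves open which parameter is to be used.

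Three stronger readings are tempting and are not supported:
- A reader might infer that the analyte is undefined. Sections 1.2 and 7.2 point to EAA, and 7.2 to peak EAA. Only formal designation is missing.
- A reader might infer that the plan inflates the AUROC by picking the best of five parameters. Section 7.1 assesses all five and plans no such choice. The 17% to 28% describes a hypothetical later analysis; it is a reason to prespecify, not a consequence of the plan.
- A reader might infer that ANOVA is wrong for the study. It suits hypothesis 1 and the group-level reading of hypothesis 2.

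**Conclusion.** The concern holds in a limited form: if hypothesis 2 is meant as a claim about distinguishing subjects, 7.1 contains no analysis that measures it, and a significant ANOVA would not show it. At the significance threshold, the AUROC is 0.74 to 0.78 and 29% to 32% of subjects are misclassified at the midpoint. In the unadjusted case, the logit interval includes 0.50. Even at d = 1.6, which the protocol offers for a different contrast, the interval is 0.61 to 0.97.

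These figures rest on equal-variance normality, 10 completers per group and the Hanley-McNeil standard error. The simulated figures also rest on the assumed correlations. Hypothesis 1, the sample size and data collection are unaffected. The change is worth making because it is cheap and determines what can be concluded on one of two stated hypotheses.

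**What to change.** In 7.1, add for hypothesis 2:
- Designate peak total EAA, in line with the sizing variable in 7.2, as the lead parameter.
- State before any results are seen which direction indicates sarcopenia. Neither 2.0 nor 7.2 gives one.
- Report its AUROC with a logit-scale 95% CI (for example DeLong) for sarcopenic versus non-sarcopenic elderly as the key contrast, and separately for sarcopenic versus young. Label both exploratory.
- Say what will be reported if the groups separate completely, since DeLong then gives no usable interval (2.8% of simulated studies at d = 1.6).
- State that no discrimination claim will rest on ANOVA p-values.

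Alternatively, if only group differences are intended, reword hypothesis 2 as a group-level aim.

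The cost is a few lines and one analysis of data already being collected, or one reworded sentence. The downside is that intervals at 10 per group are wide, so the AUROC describes the sample and cannot confirm a diagnostic claim.

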3.0 Study Design and Procedures

We will enroll up to 35 subjects with a goal to study up to 30 healthy male and females: a group of 10 whose age is between 18 and 30 years, a group of 10 whose age is 70-89 years without the presence of sarcopenia, and a group of 10 whose age is 70-89 years with sarcopenia. We will use a 5-hour (one hour prior and 4 hours post-consumption of an amino acid supplement) period to completely characterize the plasma amino acid response to 10 grams of free-form essential amino acids of which 10% of the leucine content has been enriched with L-[1-13C] leucine. The principal end-point will be plasma amino acid response over the 4 hours following the consumption of the study product.

Secondary endpoints include body composition and total body water measurements. Small shifts in fluid from the extracellular to intracellular space likely correspond with EAA appearance and disappearance in plasma. BIA is a non-invasive, rapid assessment that is sensitive to acute shifts in fluid that are associated with disease and malnutrition states, such

Version #: 10 IRB# 262590 Page 7

Date: 31May22

Institution: UAMS

Sponsor: UAMS/TRI

as sarcopenia. As an exploratory analysis, we will measure acute shifts in total body,

intracellular, and extracellular fluid using multifrequency BIA throughout visit 2. This will serve

as preliminary data on a potential non-invasive method to evaluate muscle quality, anabolic

resistance, and a proxy indicator of sarcopenia.

3.1 Study Visits

Visit 1: subjects will come to the UAMS TRI for informed consent discussion. Once consent is

obtained, subsequent study procedures will be performed. A medical history including allergies

and list of current medications will be obtained. Females of child bearing capacity will be asked

to provide a urine sample for pregnancy testing prior to the DEXA scan. Exceptions will be

made for women who have recently (past week) or currently are menstruating, have an

implanted uterine device, or women who are celibate. Urine samples will be sent to LabCorp.

Subjects will be asked to perform the following tests and measurements at visit 1:

Standing height without shoes (in cm),

Body weight without shoes (in kg),

Handgrip strength testing of their dominant hand (3 reps, in kg),

10-meter usual gait speed test,

5-rep timed chair stand test,

SARC-F (paper) questionnaire (older subjects only).

If subject meets the requirements (fasted for at least 8 hours, caffeine-free for at least 12

hours, and did not perform strenuous exercise during the past 24 hours) to perform the DEXA

scan and In Body scan on visit 1, these tests will be performed at that time. If they do not,

these tests will be performed at Visit 2.

Visit 2 (approximately 1 week after visit 1): Subjects return to the UAMS TRI having fasted for

at least 8 hours, avoided caffeine for at least 12 hours, and avoided strenuous exercise during

the past 24 hours. They will be asked about any adverse events since last visit. The In Body

and DEXA scans will be performed if these were not done at visit 1. Prior to the IV insertion, an

In Body scan will be performed if not already performed on this visit.

Version #: 10

IRB# 262590 Date: 31May22 Page 8 The study nurse will insert an IV catheter into a vein of one of the subjects' arms to use for periodic blood sampling, warming the arm by means of a heating pad or a heated plastic box. After an initial blood sample is obtained, a timer is started and blood samples and In Body scans will be obtained according to the schedule below. The study product (dissolved in ~10 ounces of water along with the stable isotope L-[1-13C] leucine) is served directly after the third blood sample. Subjects are asked to consume the drink within 1 minute.

Using a mask that covers their mouth and nose, subjects exhaled breath will be collected to measure the appearance of the labelled carbon in the leucine isotope in expired CO₂. The mask will be worn for approximately 2 minutes prior to every blood sample time point after the initial sample. A 1-2 minute period of breath analysis will occur at the designated blood sample collection times. The mask can remain off between collection periods.

At the conclusion of 5 hours elapsed time, the IV catheter will be removed and the site dressed with a bandage. A snack and beverage will be offered to the subject. Subject will then be free to leave.

Elapsed time (min., approximate)	Procedure
-0	Blood sample (~4mL into an EDTA tube)
30	In Body scan
60	Blood sample (~4mL into an EDTA tube), ,
	breath analysis, In Body scan
75	Blood sample (~4mL into an EDTA tube),
	ingest study supplement, breath analysis, In
	Body scan
90	Blood sample (~4mL into an EDTA tube)
	breath analysis, In Body scan
105	Blood sample (~4mL into an EDTA tube)
	breath analysis
120	Blood sample (~4mL into an EDTA tube)
	breath analysis, In Body scan

135	Blood sample (~4mL into an EDTA tube)
	breath analysis
150	Blood sample (~4mL into an EDTA tube)
	breath analysis, In Body scan
165	Blood sample (~4mL into an EDTA tube)
	breath analysis
180	Blood sample (~4mL into an EDTA tube)
	breath analysis, In Body scan
200	Blood sample (~4mL into an EDTA tube)
	breath analysis
210	In Body scan
220	Blood sample (~4mL into an EDTA tube)
	breath analysis
240	Blood sample (~4mL into an EDTA tube)
	breath analysis, In Body scan
270	Blood sample (~4mL into an EDTA tube)
	breath analysis, In Body scan
300	Blood sample (~4mL into an EDTA tube)
	breath analysis, In Body scan

